#### 3.3.1.3.1.3 If the treatment is exhibiting efficacy **and** the subject wants to continue for potential benefit of lapatinib therapy after being informed of the results of liver chemistry testing, then the lapatinib may be re-started at the reduced dose agreed upon by the investigator and the Study Chair. The liver event CRF should be completed and liver chemistries and aforementioned signs and symptoms should

be monitored at a minimum of every 2 weeks until resolution, stabilization, or a return to baseline values, at which point monitoring should be continued per protocol.

3.3.1.3.1.4 If a subject experiences  $ALT > 3 \times ULN$  but  $< 5 \times ULN$  and total bilirubin  $\leq 2 \times ULN$ , without signs or symptoms of hepatitis or hypersensitivity, **and** who can be monitored weekly, then the following actions should be taken:

- continue investigational product;
- monitor weekly until liver chemistries resolve, stabilize, or return to within baseline, then monitor liver chemistries as per protocol assessment schedule;
- if  $ALT > 3$  and  $< 5 \times ULN$  for  $> 4$  weeks, discontinue the treatment;
- if at any time this subject meets any of the aforementioned liver chemistry stopping criteria, then proceed as described above.

3.3.1.3.2 Liver Chemistry Follow up Criteria

3.3.1.3.2.1 For all subjects who meet any of the liver chemistry criteria described above, make every attempt to carry out the liver follow up assessments described below:

- Viral hepatitis serology including:
  - Hepatitis A IgM antibody;
  - Hepatitis B surface antigen and Hepatitis B Core Antibody (IgM);
  - Hepatitis C RNA;
  - Cytomegalovirus IgM antibody;
  - Epstein-Barr viral capsid antigen IgM antibody (or if unavailable, obtain heterophile antibody or monospot testing);
  - Hepatitis E IgM antibody (if subject resides or has travelled outside USA or Canada in past 3 months);
- Serum creatine phosphokinase (CPK) and lactate dehydrogenase (LDH);
- Complete blood count with differential to assess eosinophilia;
- Record the appearance or worsening of clinical symptoms of hepatitis, or hypersensitivity, fatigue, decreased appetite, nausea, vomiting, abdominal pain, jaundice, fever, or rash as relevant on the AE report form;
- Record use of concomitant medications, acetaminophen, herbal remedies, other over the counter medications, or putative hepatotoxins, on the concomitant medications report form;
- Record alcohol use on the liver clinical evaluation case report form.
- Refer to Appendix **12.5** for a liver safety algorithm detailing stopping and follow up criteria.

### 3.3.1.4 Cardiac Assessments

#### 3.3.1.4.1 Cardiac Definitions

##### 3.3.1.4.1.1 Cardiac Death is defined as either:

- Cardiac death due to heart failure, myocardial infarction, or arrhythmia.
- Probable cardiac death defined as sudden, unexpected death within 24 hours of a definite or probable cardiac event.

3.3.1.4.1.2 Severe symptomatic CHF is defined as New York Heart Association (NYHA) Class III or IV (Class III defined as being not capable of climbing one flight of stairs and class IV defined as having symptoms at rest) and a drop in LVEF of more than 10 points from the baseline and to below 50%. In these cases there is *no need* to perform a confirmatory second LVEF assessment. The method used for the LVEF assessment must be the same method as used for the baseline assessment.

3.3.1.4.1.3 Asymptomatic (NYHA I) or mildly symptomatic (NYHA II) is defined as a significant drop in LVEF, confirmed by a second LVEF assessment within approximately three weeks showing also a significant drop in LVEF. A significant drop is defined as an absolute decrease of more than 10 points below the baseline LVEF and to below 50%. The method used for LVEF assessment must be the same method used for the first (baseline) assessment.

#### New York Heart Association Functional Classification

I	No Symptoms and no limitations in ordinary physical activity.
II	Mild Symptoms and slight limitation during ordinary activity. Comfortable at rest.
III	Marked limitation in activity due to symptoms, even during less-than-ordinary activity. Comfortable at rest.
IV	Severe limitations. Experiences symptoms even while at rest.

##### 3.3.1.4.1.4 Stopping and holding rules

- Stopping rule

Treatment with any of the treatment regimens defined for this study will be permanently stopped if a patient develops a symptomatic cardiac event or an asymptomatic event confirmed by repeat evaluation. However, patients will remain in the study and all efforts will be made to complete all assessments as planned.

- Treatment

It is strongly recommended that patients who have symptomatic decreases in LVEF or those who meet the criteria for stopping treatment seek cardiologic consultation for advice on potential treatment for their cardiac dysfunction.

### 3.3.2 Temozolomide

**3.3.2.1** Dosing is based on adverse events (AEs) during the prior treatment cycle. If multiple AEs are seen, the dose administered should be based on the dose reduction required for the most severe grade of any single AE.

Dose Level	Dose mg/m^2	Remarks
- 2	75	Reduction if prior AE
-1	100	Reduction if prior AE
0	125	Starting dose for cycle 1 and 2, increase to 150 mg/m  for cycle 3 and beyond if non hematologic toxicity $\leq$ grade 2 and hematologic toxicity $\leq$ grade 1
+1	150	Highest possible dose level

**3.3.2.1.1** First and Second Cycle: Temozolomide will be started at a dose of 125mg/m^2/day.

**3.3.2.1.2** Third Cycle: The dose of temozolomide will be determined according to: (1) treatment related non-hematologic AE during the preceding treatment cycle, as well as (2) the worst ANC and platelet counts.

**3.3.2.1.3** Delay: On day 1 of each cycle (within the prior 72 hours), ANC  $\geq$  1.5 x 10^9/L, platelet count  $\geq$  100 x 10^9/L and all grade 2, 3 or 4 non-hematologic AEs (except for alopecia, nausea, and vomiting) must have resolved (to grade  $\leq$  1).

**3.3.2.1.4** If AEs persists, treatment should be delayed by 1 week for up to 4 consecutive weeks. If, after 4 weeks of delay, all treatment related AEs have still not resolved (to grade  $\leq$  1): then any further treatment with temozolomide should be stopped.

**3.3.2.1.5** Dose Escalations and Reductions: If, during the first and second cycle, all hematologic AEs observed were  $\leq$  grade 1 and treatment related non-hematologic AEs observed were grade  $\leq$  2 (except alopecia, lymphopenia, nausea and vomiting) then the temozolomide dose should be escalated to dose level 1 and this dose should be used as the starting dose for subsequent cycles. If treatment after cycles 1 and 2 temozolomide has to be delayed because of ongoing non-hematologic AEs of grade  $\geq$  2, then no escalation is possible. If the dose was not escalated at cycle 3, then the dose should not be escalated in further cycles (4-24).

**3.3.2.1.5.1** Dose reductions: If any treatment related non-hematologic AE observed was grade  $>$  2 (except alopecia, lymphopenia, nausea and vomiting) and/or if platelets  $<$  50 x 10^9/L and/or ANC  $<$  1 x 10^9/L, then the dose should be reduced by one dose level. Patients who require more than two dose reductions will have treatment stopped.

If any treatment-related non-hematologic AE observed was grade 4 (except alopecia, lymphopenia, nausea and vomiting) then temozolomide treatment should be stopped.

**3.3.2.1.5.2 Subsequent cycles (4-24):** Any dose reductions of temozolomide will be determined according to: (1) non-hematologic AE during the preceding treatment cycle, as well as (2) the lowest ANC and platelets observed. No dose escalation should be attempted. The same dose reductions as for the second cycle should be applied. **Important:** If the dose was reduced or delayed for AEs, there will be no dose re-escalation in subsequent treatment cycles.

**3.3.2.2 Summary of Dose Modifications or Discontinuation for Temozolomide-Related Adverse Events**

Worst Treatment-Related Non-Hematologic AE (except for alopecia, nausea, and vomiting) During the Previous Cycles	
Grade	Dose Modification
0-2	No dose modifications for non-hematologic AEs. Dose reductions based on ANC and platelet counts are applicable.
3	Reduce by one dose level (except alopecia, nausea, and vomiting).
4	Stop (except alopecia, nausea, and vomiting). Dose modifications based on ANC and platelet counts are not applicable.

**3.3.2.3 Worst Treatment-Related Hematologic AE During the Previous Cycle**

Worst AE		Platelets		
		<math>\geq 100 \times 10^9/L</math>	<math>50 - 99 \times 10^9/L</math>	<math>< 50 \times 10^9/L</math>
	<math>\geq 1.5 \times 10^9/L</math>	Dose unchanged	Dose unchanged	Reduce by 1 dose level
ANC	<math>\geq 1 & < 1.5 \times 10^9/L</math>	Dose unchanged	Dose unchanged	Reduce by 1 dose level
	<math>< 1 \times 10^9/L</math>	Reduce by 1 dose level	Reduce by 1 dose level	Reduce by 1 dose level

**Note:** A complete blood count must be performed on days 14 and 28 ( $\pm$  72 hours) after the first daily dose of each treatment cycle.

Hematologic AE on Day 1 of Each Cycle (within the prior 72 hours before Day 1)	
AE	Delay
ANC <math>< 1.5 \times 10^9/L</math> and/or Platelet count <math>< 100 \times 10^9/L</math>	Delay up to 4 weeks until all resolved. If unresolved after 4 weeks then stop. If resolved, dose delay/reductions based on non-hematologic AEs are applicable. If treatment has to be delayed for AEs, then no escalation is possible.

Non-Hematologic AE (except for alopecia, nausea, and vomiting) On Day 1 of Each Cycle (within the prior 72 hours)	
Grade	Delay

2-4	Delay up to 4 weeks until all resolved (to grade $\leq 1$ ). If unresolved after 4 weeks, then stop. If resolved, dose delay/reductions based on ANC and platelets are applicable. If treatment has to be delayed for AE, then no escalation is possible.
------------	---

### 3.3.3 Instructions on Missed Dose

- Patients should be instructed to take the medication as soon as it is remembered.
- The next due dose should be taken no sooner than 12 hours after the previous dose, and the time of administration of the subsequent doses should be adjusted until it is back on its regular “am or pm” schedule.

## 3.4 LENGTH OF PROTOCOL THERAPY

3.4.1 Patients who exhibit response to protocol therapy and have not experienced any significant or intolerable toxicities may continue to receive protocol therapy up to a maximum number of 24 cycles.

3.4.2 Patients who have exhibited objective response or clinical benefit at 12 months/cycles of study agents will have the option of stopping protocol treatment at this time at the discretion of their treating physician.

3.4.3 Similarly, treating physicians will also have the option of re-starting protocol therapy on patients that had tumor recurrence after study treatment was stopped after 12 months/cycles, with the stipulation that protocol therapy is not beyond 24 months from start of treatment date.

## 3.5 QUESTIONNAIRES

The MDASI-BT or SP (Appendix 12.7 or 12.8) will be utilized for this portion of the study. Full instruments are provided in the appendix. In addition, information regarding demographics and treatment history will be collected as part of the larger study and used in this analysis.

The MDASI-BT or SP consists of 23 symptoms rated on an 11-point scale (0 to 10) to indicate the presence and severity of the symptom, with 0 being “not present” and 10 being “as bad as you can imagine.” Each symptom is rated at its worst in the last 24 hours. Symptoms included on the instrument include those commonly associated with cancer therapies, those associated with increased intracranial pressure, and those related to focal deficits. The questionnaire also includes ratings of how much symptoms interfered with different aspects of a patient’s life in the last 24 hours. These interference items include: general activity, mood, work (includes both work outside the home and housework), relations with other people, walking, and enjoyment of life. The interference items are also measured on 0 - 10 scales. The average time to complete these instruments is 5 minutes. The MDASI-BT or SP has been translated into 18 languages [17, 20].

### 3.6 STUDY CALENDAR

STUDIES TO BE OBTAINED	Pre-Study (within 14 days of study registration)	Course 1 and 2 ( $\pm$ 3 days)	Courses 3-24 ( $\pm$ 3 days)	Discontinuation - Completion of Therapy, and/or Post Protocol Therapy
Consent & HIPAA Authorization	X 			
History	X			
Physical Exam (Ht, Wt, BSA, VS)	X	X 	X 	X
KPS Performance Status	X	X 	X 	X
Neurologic Exam	X	X 	X 	X
CBC, differential, platelets	X	X  , X 	X 	X
PT, PTT, INR 	X	X  , X 	X 	X 
Serum Pregnancy Test ( $\beta$ -HCG)	X			
Total Protein, Albumin, Ca++, PO 4 , Glucose, BUN, Serum Creatinine, Uric Acid, Alkaline Phosphatase, LDH	X	X  , X 	X 	X
SGPT (ALT), Total Bilirubin	X	X 	X 	X
Echocardiogram or MUGA	X		X 	X
EKG 	X			
MRI head and/or spine with gadolinium	X		X 	X  , X 
MDASI Symptom Assessment	X		X 	X
Collect Treatment Diary and perform Pill Counts			X 	X
Patient status assessment				X  , X 

8 weeks (except for Ht).

 Every 2 weeks.

 Every 4 weeks.

 For patients with stable disease or response, MRI surveillance should continue every 2 months for 1 year after treatment completion, then every 3 months for 1 year, then every 4 months for 1 year, then every 6 months until progressive disease, lost to follow-up or death. For patients who develops progressive disease while on follow-up under the “off treatment follow-up schedule”, reference section 3.7.9 for instructions.

 Patients removed from the study for disease progression or treatment-related toxicity should continue to be followed with quarterly updates of treatment regimens, disease status and survival.

 To be completed within +/- 1 week of the MRI assessment date.

1  
Ev  
ery

 Only for patients receiving warfarin and performed at baseline, bi-monthly for the duration of protocol therapy, at discontinuation of lapatinib and a minimum of (1 more lab draw) 2 weeks following discontinuation of lapatinib.

 EKG will be performed at baseline, and as clinically indicated during the study

 To be obtained at pre- study. Timing for obtaining consent is not limited to “within 14 days of study registration”.

 Labs (chemistry, coagulation and hematology) does not have to be repeated prior to Cycle 1 as long as it is obtained within 14 days of start of treatment date.

Patients on post protocol lapatinib must have follow-up visit and MRI or CT scan every 2 months.

---

### **3.7 ON STUDY EVALUATION**

- 3.7.1 Physical Exam to include, Vital Signs, a neurologic examination, and KPS Performance status, will be performed every 8 weeks prior to initiation of every other cycle of therapy (i.e prior to cycle 3, cycle 5, cycle 7 etc.) and when therapy is discontinued. Patient treatment diaries will be collected and pill counts will be performed prior to every other cycle of therapy and when therapy is discontinued.
- 3.7.2 Total protein, albumin, calcium, phosphorus, glucose, BUN, creatinine, uric acid, alkaline phosphatase, LDH, and when appropriate, anticonvulsant levels will be performed prior to initiation of treatment and before each course of therapy.
- 3.7.3 MRIs will be done before every other course of treatment (prior to cycle 3, 5, 7. etc.).
- 3.7.4 MDASI-BT and/or SP at the time of clinical evaluation with MRI as long as the clinical therapy is being administered (Appendix 12.7 or 12.8).
- 3.7.5 A CBC with differential and platelets will be obtained every 2 weeks.
- 3.7.6 Hepatic Monitoring: SGPT (ALT), total bilirubin levels will be performed:
  - During treatment phase: every 4 weeks, prior to each course of therapy, for the duration of chemotherapy administration (or more frequently, if clinically indicated)
  - During post-treatment phase: continue to monitor any liver chemistry abnormalities noted during treatment or within 30 days after last dose of lapatinib until values return to normal or baseline
  - bilirubin fractionation (when testing is available) is recommended if total bilirubin >2 x ULN
  - See section 3.7.6 and Appendix 12.5 for Liver Chemistry Stopping and Follow-up criteria in the presence of abnormal LFT results.
- 3.7.7 Cardiac Monitoring:
  - LVEF will be assessed every 8 weeks (2 cycles) by Echo or MUGA (MUGA preference as clinically indicated) scan. The method of evaluation used for the

LVEF assessment in an individual subject must be the same method used at baseline and throughout the duration of the trial.

- Echo or MUGA (if clinically indicated) studies must be performed under the supervision of an experienced cardiologist, presumably at the same high-volume laboratory for the duration of the trial. The guidelines of the American Society of Echocardiography will be used. These guidelines can be located on the www at <http://www.asecho.org/Guidelines.php>
- Subsequent scheduled LVEF assessments must be performed as per Appendix 12.6, “LVEF Assessment Algorithm”.
- In addition, any subject who develops clinical signs and symptoms of cardiac failure should undergo an LVEF assessment and ECG.

3.7.8 After enrollment on the clinical trial, patients will complete as baseline measures the MDASI-BT or MDASI-SP. The patient will continue to complete the MDASI-BT and/or MDASI-SP at the time of clinical evaluation with MRI as long as the clinical therapy is being administered, unless clinical deterioration makes self-report not possible before that time. The time when patients are unable to complete the self report questionnaires will be used as part of the study analysis. The MDASI-BT and/or MDASI-SP will be completed only by the patient, unless changes in vision or weakness make this difficult. If this occurs, then the caregiver or research assistant may read the questions to the patient or assist with marking the severity number or score as described by the patient. A patient caregiver may complete the questionnaires as a patient-preference proxy if the patient’s deficits preclude self report.

3.7.9 Off treatment follow-up will continue on the following schedule until the patient meets off study criteria.

3.7.9.1 For patients with stable disease or response, MRI surveillance should continue every 2 months for 1 year after treatment completion, then every 3 months for 1 year, then every 4 months for 1 year, then every 6 months until progressive disease is noted, death or lost to follow-up.

3.7.9.2 Patients removed from study treatment for disease progression or treatment-related toxicity should continue to be followed with quarterly (every 3 month) updates of treatment regimens, disease status and survival.

3.7.9.3 Stable disease (SD) patients who develops progression while being followed on the “off treatment follow-up schedule”, will continue with follow-up requirements on the PD off treatment follow-up schedule, until patient meets off study criteria.

## **3.8 CRITERIA FOR REMOVAL FROM PROTOCOL THERAPY AND OFF STUDY CRITERIA**

### **3.8.1 Criteria for Removal from Protocol Therapy**

A genuine effort must be made to determine the reason(s) why a patient fails to return for the necessary visits or is discontinued from the trial. Information regarding the reason for not completing the trial will be recorded on the appropriate case report forms.

It will be documented whether or not each patient completed the clinical study. If for any patient study treatment or observations were discontinued the reason will be recorded on the appropriate case report form. Reasons that a patient may discontinue participation in a clinical study are listed below:

Any patient who receives at least one dose of trial medication will be included in the safety analysis.

- 3.8.1.1** Evidence of recurrent or progressive disease
- 3.8.1.2** Second malignancy
- 3.8.1.3** Development of unacceptable toxicity during treatment
- 3.8.1.4** Non-adherence to the protocol
- 3.8.1.5** Refusal of therapy
- 3.8.1.6** Pregnancy
- 3.8.1.7** At 2 years of protocol therapy

**3.8.2** Off Study Criteria

- 3.8.2.1** Death
- 3.8.2.2** Lost to follow-up
- 3.8.2.3** Withdrawal of consent for continued follow-up
- 3.8.2.4** Protocol defined follow-up completed
- 3.8.2.5** Withdrawal of consent

**3.8.3** Off study procedure

*For participating CERN sites:*

When a subject is taken off-study, notify CCR study coordinator via encrypted email.  
([name] email: [[contact]](mailto:[contact]) )

**3.8.4** POST PROTOCOL THERAPY AND FOLLOW UP

**3.8.4.1** Post Protocol Single Agent Lapatinib

Patients that are showing sustained Complete Response (CR), Partial Response (PR) or Stable Disease (SD) may continue Post protocol single agent therapy with lapatinib. Post protocol lapatinib supply may be obtained through Glaxo Smith-Kline (GSK), using the same drug ordering mechanism as detailed in section 10.2.12 (Agent Ordering/Requests).

### **3.8.4.2 Post Protocol Follow Up**

Patients on post protocol single agent lapatinib will have follow up visits every 2 months for survival assessment and radiographic evaluation of disease per MRI or CT scan.

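### For patients who continue lapatinib after protocol therapy, the text does not secure 4-weekly ALT/bilirubin testing; read naturally, the schedule gives a liver panel about every 2 months

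*Combined protocol and SAP*

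**What the plan says.** Patients with sustained CR, PR or SD may go on to single-agent lapatinib, obtained "using the same drug ordering mechanism as detailed in section 10.2.12" (3.8.4.1). No limit on its duration is stated.

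- **Visits in this phase.** Section 3.8.4.2, repeated in the Précis and in 3.1, says: "Patients on post protocol single agent lapatinib will have follow up visits every 2 months for survival assessment and radiographic evaluation of disease". Calendar footnote 11 says: "Patients on post protocol lapatinib must have follow-up visit and MRI or CT scan every 2 months". None of these four statements mentions liver chemistry.
- **Liver testing during treatment (3.7.6).** ALT and total bilirubin are due "every 4 weeks, prior to each course of therapy, for the duration of chemotherapy administration (or more frequently, if clinically indicated").
- **Liver testing after treatment (3.7.6).** Sites are to "continue to monitor any liver chemistry abnormalities noted during treatment or within 30 days after last dose of lapatinib" until the values settle. This follows up known abnormalities and sets no routine interval.
- **Calendar (3.6).** In the row "SGPT (ALT), Total Bilirubin", the two course columns carry footnote 3 (4-weekly). The column "Discontinuation - Completion of Therapy, and/or Post Protocol Therapy" has an X without it. Footnote 11 sits on the MRI and patient-status rows, not on the liver row.
- **Risk (10.2.21).** Lapatinib liver injury is linked to long exposure. All subjects potentially meeting Hy's Law had at least three months of treatment, and enzymes fell in most patients once the drug was stopped. For ongoing lapatinib trials, the section reports hepatic monitoring every 4 to 6 weeks during treatment.

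**The concern.** A patient on post-protocol lapatinib with normal liver tests fits neither bullet of 3.7.6 clearly. Temozolomide has stopped and no courses are defined, so the treatment-phase bullet does not plainly apply. The post-treatment bullet is anchored to the last lapatinib dose, which has not yet been taken, and covers only abnormalities already seen. A site following the written schedule could therefore test the liver less often while the hepatotoxic drug continues.

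Stopping temozolomide does not remove the hazard. In 10.2.21, 15 of the 39 hepatic cases in which a lapatinib link could not be ruled out were on lapatinib alone.

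The stopping rules in 3.3.1.3 do not replace routine testing. In a patient without symptoms they act only after an abnormal result. Once a mild ALT rise settles, 3.3.1.3.1.4 returns the patient to routine testing: "then monitor liver chemistries as per protocol assessment schedule". For this phase, that schedule states no liver interval.

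**Working it through.** The plan gives no figure to reproduce. The check has two parts: what the text implies, and what that means in tests and delay.

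**What the text implies.** There are two main readings of the last-column X.

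1. *A panel at each 2-monthly visit.* The column explicitly covers post-protocol therapy, and footnote 11 sets the visits in that phase. The physical exam, CBC, chemistries and Echo/MUGA rows carry the same plain X, so it looks like the column's convention. This is the natural reading.
2. *4-weekly testing continues.* This holds if a patient still taking lapatinib counts as being in the treatment phase. It leaves no gap, but 3.7.6 limits that phase to courses and chemotherapy, and the calendar drops the 4-weekly footnote.

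**Inputs.** 4 weeks (3.7.6); 4 to 6 weeks (10.2.21); 2 months (3.8.4.2, footnote 11).

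- Two months in weeks: 365.25 / 6 = 60.9 days; 60.9 / 7 = 8.7 weeks.
- Panels per year: 52 / interval in weeks, or 12 / 2 for 2-monthly visits.
- Longest wait from a symptom-free rise to the next scheduled test: the interval.
- Mean wait: half the interval, assuming onset at a uniformly random time between tests.

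| Schedule | Panels per year | Mean wait (weeks) | Longest wait (weeks) |
|---|---|---|---|
| 4-weekly | 52/4 = 13 | 4/2 = 2 | 4 |
| 6-weekly | 52/6 = 8.7 | 6/2 = 3 | 6 |
| 2-monthly | 12/2 = 6 | 8.7/2 = 4.3 | 8.7 |

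**Difference between 2-monthly and 4- to 6-weekly.**

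- Panels: 8.7 − 6 = 2.7 to 13 − 6 = 7 fewer per patient-year.
- Mean delay: 4.3 − 3 = 1.3 to 4.3 − 2 = 2.3 weeks longer.
- Longest delay: 8.7 − 6 = 2.7 to 8.7 − 4 = 4.7 weeks longer.

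**The case against.** The strongest reply is that testing is already covered. The post-treatment bullet of 3.7.6 counts from the last lapatinib dose, so a patient still on the drug is in the treatment phase. Section 10.2.21 speaks of monitoring during treatment with no chemotherapy limit, and 3.7.6 allows extra tests when clinically indicated. This reading is possible and would close the gap. The text does not secure it, and the reference to chemotherapy points the other way. Testing when indicated is discretion, not a schedule.

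Other points on that side:

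- **Appendix 12.5.** Only its heading appears in the text available. Its title concerns stopping and follow-up, but an interval there cannot be ruled out. This stands as a caveat.
- **Post-protocol care.** The drug is commercial grade, and a short schedule that leaves routine laboratory work to the treating physician is defensible. However, the trial supplies the route to the drug and sets the visits, so it can also state the liver interval.
- **Prior exposure.** Many patients would enter after 12 to 24 cycles with 4-weekly panels, and 10.2.21 does not say that risk keeps rising after one or two years. This limits the likely harm but gives no reason to test less often.
- **Strength of the benchmark.** The 4 to 6 weeks in 10.2.21 is reported for ongoing lapatinib trials, not laid down as a rule for this phase.

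A reader might infer more than the documents support:

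- *That testing falls to a single panel at discontinuation.* The X sits in a column that also covers post-protocol therapy, with 2-monthly visits, and the same mark serves the other assessments there.
- *That many rises would already have outlasted the 4-week limit for ALT of 3 to 5 × ULN when found.* That rule in 3.3.1.3.1.4 runs under weekly monitoring after detection, so its clock does not start at unseen onset.
- *That patients enter this phase at about 12 weeks, the minimum for a stable-disease designation.* The described stopping points are 12 months/cycles (3.4.2) and 2 years (3.8.1.7).
- *That cardiac monitoring has the same gap.* Two-monthly visits nearly match the 8-weekly LVEF interval: 12/2 = 6 against 52/8 = 6.5 assessments a year.

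**Conclusion.** The concern holds as a minor-to-moderate safety clarification. The text shown does not carry 4-weekly ALT/bilirubin testing over to post-protocol lapatinib, and its natural reading is a panel about every 8.7 weeks. That means 2.7 to 7 fewer panels per patient-year than 4- to 6-weekly testing. A symptom-free rise would be detected 1.3 to 2.3 weeks later on average and 2.7 to 4.7 weeks later at most.

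These figures assume a panel at every 2-monthly visit, no unscheduled tests, and onset at a random time between tests. If 4-weekly testing was intended to continue, or if Appendix 12.5 sets the interval, only the wording needs attention.

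Absolute harm cannot be estimated, because the documents give neither the number of patients continuing nor a hepatic event rate for this phase. Accrual is closed, so the benefit is to patients still taking post-protocol lapatinib or moving to it. No endpoint or trial conclusion is affected.

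**What to change.** 1. In 3.7.6, replace the clause that limits 4-weekly testing to chemotherapy with: *for as long as lapatinib is given, including post-protocol lapatinib*.
2. In 3.8.4.2, add ALT and total bilirubin at a stated interval within 4 to 6 weeks.
3. Put the same interval as a footnote on the ALT/bilirubin cell of the last calendar column.

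Use one interval in all three places. If 6-weekly is preferred for this phase, 3.7.6 must say so, since it otherwise reads 4-weekly. If Appendix 12.5 already sets an interval for these patients, cite it instead.

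The cost is a short amendment for a blood test already in the trial. Compared with 2-monthly testing it adds about 3 draws per patient-year at 6-weekly and 7 at 4-weekly, some of them between visits.
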